## PROTOCOL AMENDMENT SUMMARY OF CHANGES TABLE

Document History		
Document	Date	Type of amendment
Original Protocol	15 Dec 2023	Not applicable

Public Copy

This document cannot be used to support any marketing authorization application and any extensions or variations thereof.

## 1            **PROTOCOL SUMMARY**

### 1.1           **Synopsis**

#### **Protocol title:**

A multicenter, open-label, outpatient study to evaluate the safe and effective use of a zilucoplan auto-injector combination product for subcutaneous self-administration by study participants with generalized myasthenia gravis

#### **Short title:**

An open-label, outpatient study to evaluate the safe and effective use of a zilucoplan auto-injector for self-administration by study participants with generalized myasthenia gravis

#### **Rationale:**

Myasthenia gravis (MG) is a serious, sometimes life-threatening, debilitating condition associated with numerous symptoms including muscular weakness and fatigue. Some patients can manage their symptoms with oral medications such as oral acetylcholinesterase inhibitors, corticosteroids, or nonsteroidal immunosuppressants. In addition, intravenous immunoglobulin G and plasma exchange treatment could be utilized. For those whose symptoms are not well managed by these medications, a potential alternative is long-term treatment with approved intravenous (IV) C5 inhibitors (eg, eculizumab or ravulizumab) which have proven effective at treating MG symptoms.

Zilucoplan (RA101495; ZLP) was recently approved in the US and EU and is currently available as a prefilled syringe (PFS) for subcutaneous injection (sc). The PFS reduces drug administration burden and can be used by patients with difficult venous access or who are in underserved or rural populations where economic access to IV infusions is prohibitive. However, it is expected that there will be a need to have different treatment administration options available for the administration of ZLP and that individuals may prefer to have the option to administer their ZLP medication using an auto-injector (AI). The AI device may improve the handling of the drug administration and improve compliance. DV0013 will, therefore evaluate the safe and effective self-administration with the zilucoplan-auto-injector (ZLP-AI) as an administration option.

## Objectives and estimands/endpoints

Objectives	Estimands/endpoints
Primary	

 
To evaluate the effectiveness of ZLP-AI self-administration
 
	
Primary estimand
 
 
Treatment: Zilucoplan
 
Target Population: Participants aged <math>\geq 18</math> years with gMG, already treated with zilucoplan (currently participating in MG0011 or treated with commercial zilucoplan)
 
Endpoint: Effective self-administrations of zilucoplan using the ZLP-AI from Visit 1 to Visit 8. Effective self-administration is defined as: 
 
Complete dose delivery: completeness of the delivery as confirmed by the Investigator. The entire dose of IMP should be completely delivered (ie, the yellow plunger that can be seen through the device window should be completely depressed)
 
 
 
Intercurrent event: 
 
No intercurrent event is defined
 
 
 
Population level summary: 
 
Proportion of effective self-administrations overall (total number of self-administrations from Visit 1 to Visit 8), along with the 95% CI
 
 
 

Secondary	

 
To evaluate the effectiveness of ZLP-AI self-administration using additional effectiveness endpoints
 
	
Secondary estimands
 
 
Treatment: Zilucoplan
 
Target Population: Participants aged <math>\geq 18</math> years with gMG, already treated with zilucoplan (currently participating in MG0011 or treated with commercial zilucoplan)
 
Endpoints: 
 
Effective self-administration of zilucoplan using ZLP-AI at Visit 8. Effective self-administration is defined as complete dose delivery.
 
Effective self-administration of zilucoplan using ZLP-AI at Visit 1. Effective self-administration is defined as complete dose delivery 
 
Complete dose delivery: completeness of the delivery as confirmed by the Investigator. The entire dose of IMP should be completely delivered (ie, the yellow plunger that can be seen through the device window should be completely depressed)
 
 
 
 
 

Objectives	Estimands/endpoints
	
 
Intercurrent event handling: 
 
No intercurrent event is defined
 
 
 
Population level summary: 
 
Proportion of participants, along with the 95% CI
 
 
 

 
Evaluate the safety and tolerability of the ZLP-AI self-administrations
 
	
Secondary endpoint:
 
 
Occurrence of SAEs, TEAEs, ADEs (serious and nonserious) from Visit 1 up to the SFU Visit
 

Other objectives	

 
Evaluate the PK of the ZLP-AI for self-administration
 
	
Other PK endpoint:
 
 
Measurement of plasma concentrations for zilucoplan and main metabolites CCI
 

 
Evaluate the safety and tolerability of the ZLP-AI self-administrations
 
	
Other safety endpoints:
 
 
Occurrence of ISRs
 
Occurrence of medication errors associated with adverse reaction
 

 
Evaluate the safety of the ZLP-AI
 
	
Other safety endpoint:
 
 
Occurrence of SADEs related to the use of the ZLP-AI that would preclude continued use of the ZLP-AI for self-administration (ie, SADEs and/or SADEs leading to withdrawal from the DV0013 study)
 

 
Evaluate the structural and mechanical integrity of the ZLP-AI after completion of self-administration
 
	
Other endpoint:
 
 
Occurrence of used ZLP-AI combination products identified as having structural or mechanical integrity issues after completion of self-administration.
 
Investigator observed and reported device deficiencies. Note: An independent assessment of the structural and mechanical integrity of all used ZLP-AI devices will additionally be performed by UCB. The outcome will be reported separately from the study results.
 


 
Evaluate the study participant's experience of self-administration with ZLP-AI as assessed by the SIAQ®
 
	
Other endpoint:
 
 
Preinjection SIAQ (SIAQ PRE module) domain scores at Visit 1
 
Postinjection SIAQ (SIAQ POST module) domain scores following self-administration using the ZLP-AI at Visit 1 and Visit 8
 

Objectives	Estimands/endpoints

 
Explore the study participant's preference for zilucoplan PFS (as used in MG0011 or commercial supply) vs ZLP-AI following the use of the ZLP-AI
 
	
Other endpoint:
 
 
Patient Preference Question at Visit 8
 

ADE=adverse device effects; CI=confidence interval; gMG=generalized myasthenia gravis; IMP=investigational medicinal product; ISR=injection site reaction; PFS=prefilled syringe; PK=pharmacokinetics; SADE=serious adverse device effects; SAE=serious adverse event; SFU=Safety Follow-Up; SIAQ=Self-Injection Assessment Questionnaire; TEAE=treatment-emergent adverse event; ZLP-AI=zilucoplan-auto-injector

## Overall design

DV0013 is a Phase 3b, multicenter, open-label study to evaluate the safe and effective use of a ZLP-AI combination product for sc self-administration of ZLP solution (the IMP) by study participants with generalized myasthenia gravis (gMG), planned to be conducted in Europe and the US.

The study will aim to reflect real-world use scenarios by including participants who are already self-administering ZLP using the PFS on a once-daily dosing regimen as part of the MG0011 long-term open-label extension (OLE) study or who are on commercial ZLP treatment for at least 1 month prior to Screening.

DV0013 will consist of 9 visits (2 clinic visits and 7 remote telephone visits) and 14 self-administrations using the ZLP-AI.

## Treatment Period

- Visit 1 (Screening/Day 1): Each study participant will be provided with training by study personnel in self-administration using the ZLP-AI and will receive the written instructions for use (IFU). Following the training, the study participant will perform self-administration at the clinic using the ZLP-AI.
- Visit 2 to Visit 7: No additional training will be performed; however, the IFU will be available. The study participant will perform self-administration at home using the ZLP-AI. These visits will be remote visits using a telephone call. During the call, the Investigator will ask about the self-administration and document any adverse events and adverse device effects (AEs and ADEs), any changes in concomitant medication use, and/or medication errors occurring in the course of the self-administration. Telephone visits which would be scheduled to occur on a weekend day may be skipped, and the data for the respective days (Saturday and Sunday) will be collected on the next clinic business day (Monday).
- Visit 8: The study participant will perform self-administration at the clinic using the ZLP-AI. The Investigator will collect all used devices from participants and will check completeness of the delivery for the collected devices. All used devices will be returned to UCB for an assessment of structural and mechanical integrity.
- At Visits 1 and 8, the Investigator is required to witness and evaluate the study participant's use of the ZLP-AI, document any adverse events (AEs and ADEs) and/or

medication errors occurring in the course of the self-administration, and, following the completion of the self-administration, perform a visual inspection of the ZLP-AI to check that the yellow plunger that can be seen through the viewing window is completely depressed.

### **Safety Follow-Up Visit**

- Visit 9: For all participants, a Safety Follow-up (SFU) via telephone call, 7 days ( $\pm 3$  days) after their final study dose using the ZLP-AI, will be required. Any AEs, serious adverse events (SAEs), ADEs, or serious adverse device effects (SADEs) will be recorded. Participants who were enrolled into DV0013 from MG0011 will roll back into MG0011 on the next day following Visit 8 and will continue to be followed up as part of the MG0011 protocol. Participants who were enrolled following treatment with commercial ZLP treatment will continue with their prescribed treatment; for AEs occurring after the SFU telephone call and up to 40 days after the last administration, participants will be instructed to contact the site or follow the safety reporting according to the label.

### **Number of participants**

Participants from MG0011 or those who are currently being treated with commercial ZLP and are on a stable dosing regimen for at least 1 month will be screened at approximately 20 sites in the US and Europe in order to enroll at least 25 participants who use the ZLP-AI at Visit 1 and to obtain approximately 350 self-administrations. See Section 9.8 for the determination of sample size.

### **Treatment groups and duration**

[figure not shown]
Zilucoplan will be provided in ZLP-AI devices for self-injection using weight-bracketed dosing (ie, participants will be provided ZLP-AI devices containing fixed amounts of ZLP based on their weight, and each fixed amount will cover a range of participant weights). Participants will receive the same weight bracketed dosing as currently received in MG0011 or by prescription.

The study duration for each participant will be approximately 21 days. The end of the study is defined as the date of the last SFU phone call for the last participant in the study.

No Data Monitoring Committee will be established for this study.

1.2 Schema

Figure 1-1: Study schematic

AI=auto-injector; SFU=Safety Follow-Up

Note: \*=Participants roll back into MG0011 or go back to self-administration with commercial supply on the next day after Visit 8.

### 1.3 Schedule of Activities

**Table 1-1: Schedule of study assessments**

Period	Screening Period	Treatment Period								EW b (In-clinic)	SFU Visit c (Phone call)
		Day 1 (In-clinic)	Day 2 (Phone call) a	Day 4 (Phone call) a	Day 6 (Phone call) a	Day 8 (Phone call) a	Day 10 (Phone call) a	Day 12 (Phone call) a	Day 14 (In-clinic)		
Visit #	1	1	2	3	4	5	6	7	8		9
Day	1		2	4	6	8	10	12	14		(Final dose +7±3 days)
Written informed consent	X										
Demographic data	X										
Verification of inclusion/exclusion criteria d	X										
Vaccination history	X										
Review withdrawal criteria										X	
General medical/procedures history	X										
Physical examination e		X							X	X	
Vital signs f	X										
Urine pregnancy test (βHCG) g	X								X		
MGFA classification	X										
Contact IXRS	X								X		
Recording of concomitant medication	X		X	X	X	X	X	X	X	X	X

**Table 1-1: Schedule of study assessments**

Period	Screening Period	Treatment Period									EW b (In-clinic)	SFU Visit c (Phone call)
		Day 1 (In-clinic)	Day 2 (Phone call) a	Day 4 (Phone call) a	Day 6 (Phone call) a	Day 8 (Phone call) a	Day 10 (Phone call) a	Day 12 (Phone call) a	Day 14 (In-clinic)			
Name	Screening (In-clinic)											
Visit #			2	3	4	5	6	7	8		9	
Day			2	4	6	8	10	12	14		(Final dose +7±3 days)	
Recording of final ZLP dose and dose date taken in MG0011/commercially available ZLP prior to dosing in DV0013 h	X											
Participant completes preference question i									X			
Participant completes preinjection SIAQ (SIAQ PRE module) j		X										
C-SSRS k	X								X	X		
Dispense ZLP-AI device		X										
Participant training on self-administration with ZLP-AI device		X										
Participant self-administers ZLP with ZLP-AI device		X	X	X	X	X	X	X	X			
Study personnel evaluation of self-injection and of used ZLP-AI device l		X							X			

**Table 1-1: Schedule of study assessments**

Period	Screening Period	Treatment Period								EW b (In-clinic)	SFU Visit c (Phone call)
Name	Screening (In-clinic)	Day 1 (In-clinic)	Day 2 (Phone call) a	Day 4 (Phone call) a	Day 6 (Phone call) a	Day 8 (Phone call) a	Day 10 (Phone call) a	Day 12 (Phone call) a	Day 14 (In-clinic)		
Visit #	1		2	3	4	5	6	7	8	9	
Day	1		2	4	6	8	10	12	14	(Final dose +7±3 days)	
Participant completes postinjection SIAQ (SIAQ POST module) j		X							X		
Study personnel collect ZLP-AI devices from each participant to send to UCB for structural/mechanical integrity assessment t m		X							X		
Drug and device accountability									X		
Record TEAEs, SAEs, ADEs, SAEs, medication errors, ISR, and device deficiencies n		X	X	X	X	X	X	X	X	X	
Blood sampling for ZLP plasma concentrations o	CCI										

ADE=adverse device effect; AE=adverse event; AI=auto-injector; βHCG=beta human chorionic gonadotropin; C-SSRS=Columbia-Suicide Severity Rating Scale; EW=early withdrawal; IMP=investigational medicinal product; ISR=injection site reaction; IXRS=interactive response technology;

MGFA=Myasthenia Gravis Foundation of America; PK=pharmacokinetic; SAE=serious adverse device event; SAE=serious adverse event; SFU=Safety

Follow-Up; SIAQ=Self-Injection Assessment Questionnaire; ZLP=zilucoplan

a Telephone visits which would be scheduled to occur on a weekend day may be skipped, and the data for the respective days (Saturday and Sunday) will be collected on the next clinic business day (Monday).

b If a study participant permanently withdraws from the study, the study participant should return to the clinic for an EW Visit as soon as possible but no later than the next scheduled in-clinic visit.

c Study participant will be required to perform a SFU telephone call 7 days (±3 days) after their final study dose of ZLP using the ZLP-AI.

**Table 1-1: Schedule of study assessments**

Period	Screening Period	Treatment Period								EW b (In-clinic)	SFU Visit c (Phone call)
		Day 1 (In-clinic)	Day 2 (Phone call) a	Day 4 (Phone call) a	Day 6 (Phone call) a	Day 8 (Phone call) a	Day 10 (Phone call) a	Day 12 (Phone call) a	Day 14 (In-clinic)		
Name	Screening (In-clinic)										
Visit #	1		2	3	4	5	6	7	8		9
Day	1		2	4	6	8	10	12	14		(Final dose +7±3 days)

d Participants may rescreen twice (total of 3 screenings).

e The full physical exam will include examination of the following systems: eyes, hair, and skin; respiratory; cardiovascular; and gastrointestinal systems. The Investigator should examine the injection site at each scheduled visit for injection site reactions (eg, bruising, pain, swelling, pruritis, and hematoma). Any abnormalities should be reported as AEs. Height and weight will also be measured and recorded at Visit 1. A full physical exam will be performed at Visit 1 and Visit 8. Any findings will be reported as AEs as appropriate. Any clinically significant changes since the physical examination at Visit 1 will be recorded as AEs.

f Vital signs (sitting systolic and diastolic blood pressure, pulse rate, and temperature) are to be measured prior to blood sampling and prior to dosing, where applicable.

g For women of childbearing potential, pregnancy testing will consist of urine pregnancy tests at Visits 1 and 8 only. Pregnancy test results must be negative prior to administering IMP. Positive urinary test will be exclusionary. Participant may rescreen at a later time if pregnancy not confirmed subsequently with a serum test.

h When recording the final dose taken prior to enrolling in DV0013, the time of self-administration should also be recorded. Participants should continue on the same weight-based dose that they were self-administering in MG0011 or commercial ZLP dose they were on prior to enrolling in DV0013.

i A single question will be asked at Visit 8 postdose, assessing the study participant's preference for administration method.

j The preinjection SIAQ (SIAQ PRE module version 2.1) will be completed preinjection at Visit 1; the postinjection SIAQ (SIAQ POST module version 2.1) will be completed directly following self-injection and no later than 30 minutes postinjection at Visit 1 and Visit 8 during the study Treatment Period.

k In accordance with the draft Food and Drug Administration Suicidal Ideation and Behavior Prospective Assessment of Occurrence in Clinical Trials

l Guidance (Food and Drug Administration, Guidance for Industry, 2012) study participants will be asked to complete the C-SSRS at study visits as specified.

m At Visits 1 and 8, the Investigator will observe the participant self-administering with the ZLP-AI device. The used ZLP-AI devices will be visually inspected by the Investigator to determine if the entire dose was completely delivered (ie, the yellow plunger that can be seen through the device window is completely depressed).

n All used AI devices will be sent to UCB for assessment of structural and mechanical integrity and damage (ie, clear evidence of damage/compromised structural integrity—not superficial, cosmetic imperfections).

o Note that ADEs, SAEs, ISRs, and medication errors can only be recorded on the 14 days that the participant is using the ZLP-AI, and device deficiencies will also be collected during those 14 days. Device deficiencies will be reported via the eCRF. In addition, sites will fill out a product quality complaint form; all product quality complaints will be investigated by UCB.

p A single PK sample will be collected **CC1**.

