**Table 3-1: Objectives and estimands/endpoints**

Objectives	Estimands/endpoints

 
Evaluate the study participant's experience of self-administration with ZLP-AI as assessed by the SIAQ®
 
	
Other endpoint:
 
 
Preinjection SIAQ (SIAQ PRE module) domain scores at Visit 1
 
Postinjection SIAQ (SIAQ POST module) domain scores following self-administration using the ZLP-AI at Visit 1 and Visit 8
 

 
Explore the study participant's preference for zilucoplan PFS (as used in MG0011 or commercial supply) vs ZLP-AI following the use of the ZLP-AI
 
	
Other endpoint:
 
 
Patient Preference Question at Visit 8
 

ADE=adverse device effect; CI=confidence interval; gMG=generalized myasthenia gravis; IMP=investigational medicinal product; ISR=injection site reaction; PFS=prefilled syringe; PK=pharmacokinetics; SAE=serious adverse event; SDE=serious adverse device effect; SFU=Safety Follow-Up; SIAQ=Self-Injection Assessment Questionnaire; TEAE=treatment-emergent adverse event; ZLP-AI=zilucoplan-auto-injector

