## **7 DISCONTINUATION OF STUDY MEDICATION AND PARTICIPANT DISCONTINUATION/WITHDRAWAL**

### **7.1 Discontinuation of study medication**

Dosing of a study participant must be immediately and permanently discontinued if:

- Study participant is diagnosed with meningococcal disease
- In the opinion of the Investigator and/or Sponsor, it is unsafe for the study participant to continue dosing with study medication (eg, suspected pancreatitis)

In circumstances where permanent discontinuation from study medication may occur, the Investigator is to discuss with the study participant the appropriate processes for discontinuation from study medication and must discuss with the study participant the options for continuation of the assessments in the SoA (Section 4.3), including different options of follow up (eg, in person, by phone/mail, in correspondence/communication with other treating physicians, from the review of medical records) and collection of data, including endpoints and AEs. Study participants who discontinue study medication should not be automatically removed from the study. Whenever safe and feasible, it is imperative that study participants remain on the study to ensure safety surveillance and/or collection of outcome data. The Investigator must document the level of follow up that is agreed to by the study participant, any changes to the scheduled visits and assessments, and the plan for follow up that is agreed to by the participant. In regard to changes to scheduled visits, for the level of follow up, it is recommended that the Early Withdrawal Visit and the SFU Visit be prioritized. If the study participant does not want to continue the study medication and withdraws consent (Section 7.2), the Investigator should contact the Medical Monitor, whenever possible, to discuss the withdrawal of a participant in advance.

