## 7.2 Participant discontinuation/withdrawal from the study

Participants are free to withdraw from the study at any time, without prejudice to their continued care.

A participant may withdraw from the study at any time at his/her own request or may be withdrawn at any time at the discretion of the Investigator for safety, behavioral, compliance, or administrative reasons.

If the participant withdraws consent for disclosure of future information, the Sponsor may retain and continue to use any data collected before such a withdrawal of consent.

If a participant withdraws from the study, he/she may request destruction of any samples taken and not tested, and the Investigator must document this in the site study records.

See the SoA (Section 1.3) for data to be collected at the time of study discontinuation and follow up and for any further evaluations that need to be completed.

Participants should be withdrawn from the study if any of the following events occur:

1. Participant develops an illness that would interfere with his/her continued participation.
2. Participant is noncompliant with the study procedures or medications in the opinion of the Investigator.
3. Participant withdraws his/her consent.
4. There is confirmation of a pregnancy during the study, as evidenced by a positive pregnancy test. If the study participant was enrolled from MG0011, the study participant should roll back into MG0011, and MG0011 protocol procedures should be followed. Participants recruited from commercial supply should go back to using commercial supply and follow the guidance in the regional-approved product label.
5. The Sponsor or a regulatory agency requests withdrawal of the participant.
6. The Investigator is of the opinion that the participant's continued participation in the study is not in the best interest of the participant.
7. Participant experiences a severe or serious injection site reaction (eg, bleeding, bruising, or pain) or a SAE that would, in the opinion of the Investigator, preclude the participant's further participation in the study.

Study participants who withdraw from DV0013, ie, study participants who have a medical condition or personal preference that precludes further self-administration, must perform a SFU telephone call or equivalent 7 days ( $\pm$  3 days) after their final DV0013 dosing visit.

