4 STATISTICAL ANALYSIS

4.1 General considerations

Statistical analysis and generation of tables, figures, participant data listings, and statistical output will be performed using SAS® Version 9.4 or higher. If a different SAS version or different software will be used during the statistical analysis, then this should be reported in the CSR. All tables and listings will use Courier New font size 9.

All study data will be presented in participant data listings. Descriptive statistics will be displayed to provide an overview of the study results. For continuous variables, descriptive statistics will include number of participants with available measurements (n), mean, standard deviation (SD), median, minimum, and maximum. For categorical variables, the number and percentage of participants in each category will be presented. Unless otherwise noted, the denominator for percentages will be based on the number of participants included in the respective analysis set.

Participants with missing data can generally be accounted for using the following approaches:

- For summaries of demographics and Baseline characteristics: summarize percentages based on all participants in the analysis set and include a “Missing” category (corresponding to participants with missing data for the variable being summarized) as the last row in the list of categories being summarized.
- For summaries of safety or other variables, unless otherwise specified: summarize percentages based only on those participants with observed data for the variable being summarized. As the denominator may be different from the number of participants in the analysis set being considered, the denominator should be displayed in the table. The general format for displaying this will be “n/Nsub (%)”.

Unless otherwise noted, all percentages will be displayed to one decimal place. No percentage will be displayed for zero counts, and no decimal will be presented when the percentage is 100%.

For the purpose of the tabulations the lower and upper confidence limits for the percentages will be truncated at 0 and 100% respectively.

For PK concentrations, summary statistics will include geometric mean, geometric coefficient of variation (CV), 95% confidence intervals (CIs) for geometric mean, arithmetic mean, SD, median, minimum, and maximum. All summaries of PK variables will be based on the observed values. No imputation will be used.

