4.1.3 Mapping of assessments performed at Early Discontinuation Visit

If a participant prematurely discontinues study intervention at any time prior to Visit 8, the participant should return to clinic for a stand-alone Early Withdrawal Visit. C-SSRS is the only assessment to be performed at that visit that will be mapped to the next scheduled visit (which is Visit 8).

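### The device-preference question is asked at Visit 8 but not at the Early Withdrawal visit, so the auto-injector's preference share could be overstated if participants leave because of the device

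*Protocol*

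**What the plan says.** **Collection.** Protocol Table 3-1 lists the endpoint as "Patient Preference Question at Visit 8", under the other (exploratory) objectives. In Table 1-1 the row "Participant completes preference question" has one mark, at Day 14, and footnote i reads "A single question will be asked at Visit 8 postdose". Section 8.1.4 gives the same timing and three answers: auto-injector, prefilled syringe, or no preference.

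**Early withdrawal.** Footnote b of Table 1-1 says that on permanent withdrawal "the study participant should return to the clinic for an EW Visit as soon as possible". The C-SSRS is marked at both Visit 8 and EW; the preference question is not marked at EW. Section 7.2 foresees withdrawal by "study participants who have a medical condition or personal preference that precludes further self-administration", and also withdrawal after a severe or serious injection site reaction.

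**Analysis.** SAP 4.4.2 summarises preference as categorical data in the Safety Set under the rules of Section 4.1. For safety or other variables, those rules "summarize percentages based only on those participants with observed data for the variable being summarized". SAP 4.1.1.2 imputes nothing and uses observed cases. SAP 4.1.3 adds that "C-SSRS is the only assessment to be performed at that visit that will be mapped to the next scheduled visit".

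**The concern.** This is the only item that asks participants to compare the auto-injector directly with the prefilled syringe. Anyone who leaves early because the auto-injector hurts, fails or is disliked would plausibly not choose it. That person may come to a clinic visit at which the question is not asked. If the percentage is then taken over observed answers, that person is absent from both numerator and denominator. The table would be labelled Safety Set but would in effect describe those who reached Visit 8. An answer not collected at the time cannot be recovered by analysis.

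What is at stake is how one exploratory descriptive percentage is read. No primary or secondary result depends on it.

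**Working it through.** **1. The plan's own figure.** Protocol 9.8 plans at least 25 participants and about 350 self-administrations; Section 4.1 gives 14 per participant. 25 × 14 = 350, which agrees. The documents state no expected preference share, withdrawal rate or power for this endpoint, so there is nothing else to reproduce.

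**2. Which denominator applies.** SAP 4.1 contains two rules. The default, unless otherwise noted, is the number in the analysis set. The rule for safety or other variables uses observed data and displays n/Nsub. Preference is classed as an other endpoint, and SAP 4.1.1.2 restricts summaries to observed cases, so the second rule is the better reading. SAP 4.4.2 does not settle it.

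**3. Formula under the observed-data rule.** Let N be the number dosed, w the number leaving before Visit 8 who are not asked and would not have chosen the auto-injector, and x the number asked who choose it.

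- Reported share: p = x/(N − w)
- Share if all had been asked: x/N = p(N − w)/N
- Overstatement: p − p(N − w)/N = p·w/N

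**4. Numbers.** N = 25 is from the protocol. The values w = 0 to 5 and p = 0.5 to 0.9 are assumptions. For w = 1 the overstatement is 0.5/25 = 2.0 points to 0.9/25 = 3.6 points. The worked example uses whole counts with p near 0.8.

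| w | Reported | All asked | Example difference (points) | Range for p = 0.5 to 0.9 (points) |
|---|---|---|---|---|
| 0 | 20/25 = 80.0% | 20/25 = 80.0% | 0 | 0 |
| 1 | 19/24 = 79.2% | 19/25 = 76.0% | 3.2 | 2.0 to 3.6 |
| 2 | 18/23 = 78.3% | 18/25 = 72.0% | 6.3 | 4.0 to 7.2 |
| 3 | 18/22 = 81.8% | 18/25 = 72.0% | 9.8 | 6.0 to 10.8 |
| 5 | 16/20 = 80.0% | 16/25 = 64.0% | 16.0 | 10.0 to 18.0 |

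**5. The opposite case.** If two participants left for reasons unrelated to the device and both favoured the auto-injector, the report would be 18/23 = 78.3% against 20/25 = 80.0%, an understatement of 1.7 points.

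**6. Scale.** The exact 95% confidence interval for 20/25 is 59.3% to 93.2%. One or two device-related withdrawals move the share by 2.0 to 7.2 points, which is well inside that interval.

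**7. Under the default denominator.** If the Safety Set number were used, the reported figure would be x/N and the overstatement would vanish. Those not asked would then be counted, without saying so, as not choosing the auto-injector.

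**The case against.** The case for leaving the plan alone has real substance.

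- **Withdrawals may be few.** Treatment lasts 14 days, in people already treated with zilucoplan and selected as willing and able to use the device (Protocol 5.1). Section 7.2 also lists reasons that say nothing about the device, such as illness, pregnancy or a sponsor request. The personal-preference wording does not name the auto-injector, and the prefilled syringe is self-administered too. This stands: overstatement is possible, not shown.
- **Stopping medication is not leaving the study.** Section 7.1 says "Study participants who discontinue study medication should not be automatically removed from the study", so some of these participants might still reach Visit 8. This stands in part. The question is labelled postdose, and SAP 4.1.3 directs anyone who stops early to a stand-alone EW visit, so it is unclear whether they would be asked.
- **A reader could see the gap.** The n/Nsub display shows how many answered, and SAP 6.2 tabulates reasons for discontinuation. This helps, but it does not supply the missing answers or link them to reasons in the preference table.
- **The limitation is declared.** Section 8.1.4 calls the data exploratory and disclaims robustness and generalizability. It does so in general terms and does not mention that early leavers are not asked.
- **A common time point is defensible.** Asking everyone after 14 uses keeps exposure comparable. This is a fair reason to show EW answers separately, but not a reason to forgo them.

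A reader might also infer that all post-injection experience data come only from completers. They do not: SIAQ POST is also completed after the first injection at Visit 1, so only its Visit 8 scores are restricted in this way.

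**Conclusion.** The gap in collection is real and easily closed; its effect is conditional. The preference question has no place at EW, nothing carries it over, and the better reading of the SAP removes early leavers from the percentage. Each withdrawal who would not have chosen the auto-injector could raise its reported share by about 2.0 to 3.6 points. That rests on N = 25, an assumed share of 50% to 90% among those asked, and the observed-data denominator.

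A reader might go further and conclude that the share is inflated, or that any bias must favour the auto-injector. The documents do not support either. They give no withdrawal rate, the effect is zero without device-related withdrawals, and unrelated withdrawals can push the share in either direction. Nor would every withdrawer necessarily be reached at EW: attendance there is worded as something participants should do, whereas Section 7.2 makes only the follow-up call or its equivalent mandatory for them.

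With an exploratory endpoint and no inference planned, this is a minor point.

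**What to change.** **Protocol.** Mark the preference question in the EW column of Table 1-1 for anyone who has used at least one ZLP-AI. Amend footnote i, Section 8.1.4 and the endpoint wording in the synopsis and Table 3-1 to *Visit 8 (postdose) or EW*.

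**SAP 4.4.2** (and the matching endpoint wording in Table 1–1). State the denominator. Report over the Safety Set with a *not asked/not answered* row, and show EW answers both pooled with Visit 8 and separately.

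No change to SIAQ POST collection is needed. It already has a Visit 1 assessment, and its 30-minute window after injection would not generally be met at EW.

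**Cost.** One question at an existing clinic visit, one schedule cell, and a few lines of text. EW answers will reflect fewer than 14 uses, hence the separate display, and some withdrawers will not attend. SAP 6.14.1 refers to an observation made during the study, so it was already under way by Amendment 1 and some EW answers may no longer be obtainable. The SAP change does not depend on them: a stated denominator and a row for those not asked would by themselves keep a Visit 8 percentage from being read as a result for everyone dosed.
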